9.3.3.2 Clinical Characteristics

- Pre-index Quan-Charlson comorbidity score—Quan-Charlson comorbidity score will be calculated based on the presence of diagnosis codes in the pre-index period (including the index date) (16). The Quan-Charlson comorbidity score will also be categorized into the following groups: zero, one to two, three to four, and five or more.
- Pre-index comorbid conditions-General comorbid conditions will be defined using the Clinical Classifications Software managed by the Agency for Healthcare Research and Quality (AHRQ) (17). This measure generates indicator variables for specific disease conditions based on diagnosis codes. The top 20 comorbid conditions will be presented.
- Pre-index antihyperglycemic medications— Pre-index antihyperglycemic medications will be identified based on written prescription, medication administration, and medication history records in the EHR data during the pre-index period. Binary flags, one per medication class and another per distinct medication based on generic name, will be created for the antihyperglycemic medications. Medication classes will be determined using the “Medication Class” column in Tables 2 through 13 of [Annex 1, Appendix B](#) and will include metformin, sulfonylureas, meglitinides, thiazolidinediones (TZDs), DPP-4 inhibitors other than linagliptin, glucagon-like peptide-1 receptor agonists (GLP-1RA), sodium-glucose co-transporter 2 (SGLT2) inhibitors, basal insulins, bolus insulins, mixed insulins, alpha glucosidase inhibitors, and amylin analogs. Combination products containing two medication classes will be considered as two distinct medication classes. Distinct medications will be determined using the “Medication Name” column in Tables 2 through 13 of [Annex 1, Appendix B](#). Combination products containing two generic ingredients will be considered as two distinct antihyperglycemic medications.

- Pre-index antihyperglycemic therapy categories—Patients will be categorized into one of the following groups based on the medication class for their pre-index antihyperglycemic therapies:
 - Metformin only
 - Sulfonylurea only
 - Meglitinide only
 - TZD only
 - GLP-1RA only
 - SGLT2 inhibitor only
 - Basal insulin only
 - Metformin + sulfonylurea
 - Other combination (additional groups will be created for any medication class combinations that are present among least 5% of the study sample)

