9.5 STUDY SIZE

This study is exploratory and not characterized with *a priori* hypotheses. All patients identified in the data that meet the inclusion criteria and do not meet the exclusion criteria will be included in the study population.

A sample size calculation was conducted to determine the minimum number of patients that would be required to detect a change in HbA1c of at least 0.5% among the cohort groups. Based on previously published studies, it was assumed that the standard deviation for the 24-

week mean change in HbA1c from baseline could range between 1.2 (based on the placebo adjusted value in the MARLINA-T2D trial (20)) and 1.5 (based on retrospective studies of diabetes treatments using electronic medical record data from across the United States (21)). Assuming a SD of 1.2 for the change in HbA1c, at least 92 patients would be needed in each of the two smallest groups of the cohort of interest (e.g., age, renal function, age by renal function) in order to have 80% power to detect a mean difference in HbA1c of at least 0.5% using a two-sided test at an alpha of 0.05. If the standard deviation for the change in HbA1c is 1.5, then 143 patients would be needed in each of the two smallest groups.

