9.7.3 Secondary Analysis

For the secondary analysis, results will be stratified by age, renal function, and race/ethnicity. Comparisons of pre-index characteristics and outcome measures across age, renal function, and race/ethnicity strata will be provided, and appropriate tests will be used based on the distribution of the measure. Continuous measures will be compared using t-tests and categorical measures will be compared using chi-square tests. P-values and 95% confidence intervals will be reported. Reported p-values will not be adjusted for multiple comparisons.

In addition, as part of the secondary analysis, multivariable modelling will be considered to assess change in HbA1c, controlling for an a priori list of covariates. The use of multivariable modelling will be dependent on having robust sample size distribution (as defined in Section 9.5 Study Size) across age and eGFR categories.

Since the primary outcome of change in HbA1c is calculated using just two timepoints, pre-index and follow-up, multivariable analysis will be conducted using ordinary least squares (OLS). In the event that the assumption that the majority of patients have only one HbA1c measure during the follow-up period turns out to be false and there are multiple HbA1c values per patient during this timeframe, mixed models repeated measures (MMRM) will be used to control for the correlation of multiple HbA1c observations from the same patient.

Following standard procedure, regression diagnostics will be performed for each model to assess goodness of fit and violations of model assumptions (e.g., multicollinearity,

heteroskedasticity). When there are violations of the model, Optum will note them and make appropriate corrections to the data (i.e., typically through transformation of either the independent or dependent variables) or in the method of estimation.

The following list of covariates will be included in the model provided sufficient sample size distribution:

- Age categories (40 to 54 years, 55 to 64 years, 65 to 74 years, and ≥ 75 years)
- Sex
- Race
- Ethnicity
- Geographic region
- Pre-index HbA1c
- Pre-index renal function categories based on eGFR (< 30 ml/min/1.73m², 30 to 44 ml/min/1.73m², 45 to 59 ml/min/1.73m², 60 to 89 ml/min/1.73m², and ≥ 90 ml/min/1.73m²)
- Pre-index Quan-Charlson comorbidity score

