- Pre-index individual comorbidities (each of the AHRQ top 20 comorbidities identified for this population will be included unless the comorbidity is already included in the Charlson Comorbidity Index)

Age and renal function categories will be assessed for adequate sample size across categories based on the sample size calculation reported in Section 9.5. If the sample size distribution is not sufficient to evaluate age as a categorical variable, age will be included as a continuous variable in the model. The eGFR categories of 45 to 59 ml/min/1.73m² (Stage 3A kidney disease) and 30 to 44 ml/min/1.73m² (Stage 3B kidney disease) will be collapsed into one category (Stage 3 kidney disease) if there is not sufficient sample to evaluate as separate categories.. If the sample size distribution is still not sufficient across the eGFR categories, then eGFR will be included as a continuous variable in the model.

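### The adjusted eGFR contrasts in 9.7.3 condition on a Quan-Charlson score from which renal disease has not been removed

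*Combined protocol and SAP*

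**What the plan says.** Section 8 makes comparison of HbA1c change between renal function categories a secondary objective. Section 9.7.3 addresses it in two ways: unadjusted tests between strata, and a conditional regression ("multivariable modelling will be considered to assess change in HbA1c, controlling for an a priori list of covariates"). The regression is OLS, or a repeated-measures mixed model if most patients have several follow-up values.

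The covariate list contains both "Pre-index renal function categories based on eGFR" and "Pre-index Quan-Charlson comorbidity score". It then adds individual conditions under one overlap rule: "each of the AHRQ top 20 comorbidities identified for this population will be included unless the comorbidity is already included in the Charlson Comorbidity Index".

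Section 9.3.3.2 says how the score is built: "Quan-Charlson comorbidity score will be calculated based on the presence of diagnosis codes in the pre-index period". It gives no items or weights. It also defines four score groups, and 9.7.3 does not say whether the number or the groups enter the model. eGFR is computed separately, from serum creatinine, age, sex and race.

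**The concern.** In this model eGFR category is the exposure. A coded kidney diagnosis largely restates that exposure and is not a confounder of it. If the score contains a renal item, the model compares eGFR groups at equal total score. A patient with eGFR below 30 who carries renal points is then set against a patient with eGFR of 90 or more who carries extra non-renal disease. The objective calls for a different comparison: eGFR groups at equal non-renal comorbidity.

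The overlap rule does not help. A kidney diagnosis that the index counts stays in the score. One that the index does not count, but that ranks in the top 20, enters as its own flag.

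Section 7 says the study is meant to show comparable effectiveness across renal function and to add information below eGFR 45. Section 9.9 expects baseline differences between the groups, so readers will lean on the adjusted result. A shift toward zero would favour comparability and a shift away would count against it. The documents do not tell us the direction.

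**Working it through.** **1. The plan's own figure, for scale.** Section 9.5 asks for "80% power to detect a mean difference in HbA1c of at least 0.5% using a two-sided test at an alpha of 0.05". With n = 2(z₀.₉₇₅ + z₀.₈₀)² × SD² / 0.5² and (1.960 + 0.842)² ≈ 7.849:

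- SD 1.2: 15.70 × 1.44 / 0.25 = 90.4, so 91. The t-test version gives 91.4, so 92.
- SD 1.5: 15.70 × 2.25 / 0.25 = 141.3, so 142. The t-test version gives 142.2, so 143.

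The stated 92 and 143 are reproduced and do not depend on the score. The 0.5-point difference is the only reference size in the plan.

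**2. Formula for the shift.** Write the score as C = O + w·R, where O is the non-renal points, R a renal code (0/1) and w its weight. In OLS on category indicators plus a linear score, each contrast equals the difference in mean outcome minus the fitted slope times the difference in mean score. Hence

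contrast using C − contrast using O = b_O·ΔO − b_C·(ΔO + w·ΔR).

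Δ is the difference between two eGFR categories; b_O and b_C are the two fitted slopes. If the slopes agree (both b), the shift is −b·w·ΔR. Its sign follows b.

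**3. Range.** None of b, w or ΔR is in the documents. All are assumed: b = 0.02 to 0.10 HbA1c points per score point, w = 1 or 2, ΔR = 0.3 to 1.0.

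- Smallest: 0.02 × 1 × 0.3 = 0.006, or 0.006/0.5 ≈ 1% of the planning difference.
- Largest: 0.10 × 2 × 1.0 = 0.20, or 0.20/0.5 = 40%.
- Slope needed for a 0.5-point shift at ΔR = 0.9: 0.5/0.9 = 0.56 (w = 1) or 0.5/1.8 = 0.28 (w = 2).
- b = 0: no shift.

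**4. Simulation check.** One million records, a reduced model with eGFR category and score only, b = 0.05, mean non-renal points 2.0 (<30) and 0.8 (≥90). Entries are the <30 versus ≥90 contrast with the full score minus the same contrast with the renal item removed.

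| Assumed coding | w = 1 | w = 2 |
|---|---|---|
| Code present in all <30 and no others | −0.050 | −0.100 |
| 90% (<30) vs 2% (≥90), code itself has no effect | −0.035 | −0.048 |
| Same coding, code acts like other points | −0.044 | −0.088 |

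The formula agrees. In row 3, 0.05 × 0.88 = 0.044 and 0.05 × 2 × 0.88 = 0.088. In row 2 the fitted slope with w = 1 drops to 0.0457, and 0.0498 × 1.2 − 0.0457 × (1.2 + 0.88) = −0.035.

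In row 2 the true contrast is zero and the full score creates a spurious one. In row 3 the full score absorbs a real renal difference.

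**5. Which categories.** The simulation assumed code prevalences of 90%, 70%, 40%, 8% and 2% from lowest to highest eGFR. With b = 0.05 and w = 1, the shifts versus ≥90 are 0.05 × 0.88 = 0.044 (<30), 0.05 × 0.68 = 0.034 (30–44), 0.05 × 0.38 = 0.019 (45–59) and 0.05 × 0.06 = 0.003 (60–89).

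**6. Against sampling error.** Section 9.7.1 gives no counts by eGFR. Assuming 500 to 1,000 patients below 30 and 3,000 at ≥90, with SD 1.5, the unadjusted standard error is 1.5 × √(1/500 + 1/3,000) = 0.073 down to 1.5 × √(1/1,000 + 1/3,000) = 0.055. The shift can be of that order, and it does not shrink as the sample grows.

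**The case against.** - **Score content is not shown.** The documents list no items or weights, so the renal item is method knowledge to be confirmed. A reader might infer that the score must rise as eGFR falls. It need not: one rests on diagnosis codes and the other on creatinine, so the link depends on coding. This stands.
- **Size is assumed.** The slopes have no source, and the simulated model leaves out baseline HbA1c and the individual conditions that 9.7.3 includes, so the plan's conditional slope may differ. This stands: the range is illustrative.
- **A definite shift is too strong.** A reader might infer that every adjusted renal difference moves by the comorbidity coefficient. That holds only with weight 1 and coding that matches eGFR category perfectly. Otherwise the shift scales with weight and coding difference, and it may be near zero.
- **Flags are different.** A kidney-disease flag has its own coefficient, so it does not impose the non-renal slope on renal disease. It is a separate over-adjustment for the exposure.
- **Scope.** The study is exploratory, the model is secondary and conditional, and the same objective also has unadjusted tests. Section 9.2.3 cites a Section 9.7.4.4 that is not in the available text, so this is the one adjusted model only in what can be read. This limits the weight of the point but does not remove it.
- **Planned diagnostics.** The multicollinearity check might flag overlap. The remedies named (transforming variables or changing the estimation method) would leave renal points in the score.

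**Conclusion.** The structural point holds. Section 9.7.3 puts eGFR category and an unmodified Quan-Charlson score in one model, and its overlap rule does not reach kidney diagnoses. Whether this counts as bias depends on the target. If the target is the eGFR difference at equal non-renal comorbidity, as the objective suggests, retaining the renal item is over-adjustment.

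Under the assumed inputs the shift is about 0.006 to 0.20 HbA1c points, mainly at eGFR below 45 and negligible if the slope is near zero. This rests on the index containing a renal item and on the score entering linearly. If the score enters in groups, renal points still move patients between groups, but the formula no longer applies.

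Two further inferences are not supported. The main results are not compromised: the descriptive primary analysis, the unadjusted comparisons and the sample size do not use the score. Nor does it follow that diabetes and diabetic-complication items should also be stripped from the main model. Section 9.9 expects longer diabetes duration at lower renal function and the model has no duration term, so those codes may be a partial proxy for it.

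**What to change.** In Section 9.7.3, for the eGFR contrasts:

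- Use a Quan-Charlson score computed without the renal-disease item(s).
- Omit any AHRQ top-20 flag that is a kidney-disease diagnosis.
- Report the model with the full published score as a sensitivity analysis.
- Keep diabetes and diabetic-complication items in the main model. A version without them can be a further sensitivity analysis.

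In Section 9.3.3.2, list the score's items and weights, and keep the full score for the descriptive tables. In 9.7.3, state whether the score enters as a number or in groups.

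The cost is a few lines of text, one recoded variable and one extra model. The downside is that the modified score is no longer the published one; the full-score sensitivity model keeps that comparison available.

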9.8 QUALITY CONTROL

To generate an accurate dataset, Optum incorporates quality assurance checks during dataset construction. Multiple checks are used by project team members throughout the dataset construction process. An additional final overall verification is performed before the dataset is released for analysis. Quality checks used include:

- Verification of sample selection
- Version control, when necessary
- Checks for dataset merge or join problems
- Review of raw data used for creation of constructed variables
 - Checks on record identifiers (e.g., uniqueness)
 - Checks for missing or out-of-range variables
 - Other edit or logic checks (e.g., verifying skip patterns, null values, flag versus continuous measures)
 - Visual checks of text fields
- Careful review of analytic variable specifications
 - Review of all constructed variable definitions by a second analyst
 - Confirmation of complex variable definitions with study experts (i.e., medical director, pharmaceutical specialist)
- Multiple checks on each constructed variable
 - Checks for missing or out-of-range variables
 - Record-level verification of all data elements for a sample of records
 - Double programming of select variables
 - Cross-tabs
 - Logic checks and code review
- Internal team review of the implementation of the dataset construction process

All amendments to the study protocol will be discussed with and agreed upon by the sponsor. Actual amendments to the study protocol will be made by the vendor and sent to BIPI for review and approval. The date of the amendments will be documented on the cover page of the study protocol.

9.9 LIMITATIONS OF THE RESEARCH METHODS

This study has several limitations inherent to its non-interventional study design. There may be baseline differences in the different age and renal function categories. In randomized clinical trials, these differences are mitigated by randomization. Among the important considerations is if there are substantial differences in baseline HbA1c. It is well known that the change from HbA1c is a function of baseline HbA1c, ie, the higher the baseline HbA1c, the greater the change from baseline even with comparable doses of the glucose lowering medication. This observation has been confirmed by Esposito et al (22) in their analyses of several DPP4 inhibitors.

Second, we have selected a follow up window of 6 months rather than a longer window e.g. up to 1 year. Maximal effectiveness is usually achieved by 6 months, although in randomized controlled trials HbA1c values may be lower at later time points. This limitation is balanced against the observation that medication persistence at 6 months will likely be

better than at 12 months and the fact that we wish to maximize the numbers of patients in each of the age and renal function cells.

Third, duration of T2DM is likely to be longer in patients with lower renal function. Increased duration of diabetes is also associated with greater reductions in beta cell function. Since one of the mechanisms of DPP4 inhibitor medications is to increase GLP-1 mediated insulin secretion, reduced renal function could theoretically be associated with diminished glycemic effectiveness. If the current study supports this observation, this will confound the claim of comparable glycemic effectiveness across the range of renal function, but it will be an important observation for the management of T2DM patients. Lajra et al reported on a retrospective analysis of 202 patients from two separate trials in which patients with > 10 years of diabetes were randomized to linagliptin 5 mg (n = 122) or placebo (n = 80)(15). The placebo adjusted mean difference in HbA1c was -0.66% (95% CI -0.85 to -0.38). No direct comparisons were made with shorter duration of diabetes. However, these data suggest that differences in duration of diabetes are unlikely to have a major effect on the data obtained in the current proposal.

Fourth, in contrast to many real world evidence studies, this study does not have an active comparator. Since all other DPP4 inhibitors require dose adjustment for declining renal function, a comparator study to show similar/different effectiveness would be difficult to design to be able to account for all the patient factors that contribute to medication distribution, elimination and dosing and likely would require an inordinately large data base.

Fifth, due to the descriptive nature of this study, multiple different comparisons are being conducted to evaluate change in HbA1c by age, renal function, and race categories. We have not adjusted our p values for multiplicity but we may perform post hoc adjustments if requested by reviewers during the publication process.

Finally, the findings from this study are expected to have limitations that are common to analyses conducted with retrospective EHR data. The possibility of misclassification exists in all studies that rely on retrospective data. Evidence of conditions and events that are based on reported diagnosis codes or procedure codes may not reflect confirmed diagnoses. While EHR data capture prescriptions written by a prescriber, it is not possible to know if patients received and adhered to their medication and there are no structured data fields to identify if and when a medication was discontinued by the patient or the provider. The EHR database does not include the entire medical chart for the patient, which raises the possibility of missing data. Unlike claims data, EHR data do not contain eligibility information and continuous eligibility is not able to be assessed. Services provided to the patient by facilities and providers outside of the healthcare systems providing EHR data to Optum will not be captured although this is not expected to be a major limitation in this study because the primary outcome, HbA1c, is likely to be measured by the same provider who wrote the patient's prescription for linagliptin. However, there may be circumstances where a patient may receive care that falls outside of their provider's electronic record system such as being treated at an out of network hospital.

Despite these limitations, EHR data are a powerful source of data for the examination of health outcomes in the "real world" setting away from the highly controlled environment of

clinical trials. This study offers the advantage of a large sample of patients with diverse demographics and medical histories.

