3. RESPONSIBLE PARTIES

4. ABSTRACT

Name of company: Boehringer Ingelheim			
Name of finished medicinal product: Tradjenta			
Name of active ingredient: Linagliptin			
Protocol date: 20-OCT-2017	Study number: 1218.182	Version/Revision: 1.0	Version/Revision date:
Title of study:	Real world glycemc effectiveness of linagliptin (Tradjenta) among type 2 diabetes mellitus adults by age and renal function		
Rationale and background:	
Patients with type 2 diabetes mellitus (T2DM) have progressive decline in renal function and this decline in function is greater than age-related decline in patients without diabetes. Selection of glucose lowering agents is often affected by the level of renal function. Dipeptidyl peptidase-4 (DPP-4) inhibitors are approved to treat hyperglycemia among adults with T2DM with a wide range of renal function. In contrast to most other DPP-4 inhibitors, linagliptin does not require dose adjustment as renal function declines. Without further requirement of dose adjustment, linagliptin affords simplicity for chronic management of HbA1c.
 
Current literature indicate that decline in renal function is also associated with glycemc control, hypertension, albuminuria and dyslipidemia. However, there is limited evidence about the real world effectiveness and safety of linagliptin across different age and renal functions among adults with T2DM.
 
For better management of hyperglycemia it is pertinent to understand the glycemc effectiveness of linagliptin among adults with T2DM with varying age and renal function who are treated in the real world setting. With a potentially larger sample size, it is possible to compare the glycemc effectiveness of linagliptin across the range of ages and renal function.
 
The aim of the current study is to compare real world glycemc effectiveness across a range of ages and renal function among adults with T2DM who are initiated on linagliptin.
		
Research question and objectives:	
The primary study objective is to:
 
 Describe change in HbA1c among adults with T2DM within 60 to 180 days following initiation of linagliptin across pre-defined age and renal function categories. Age categories will be defined as: 40 to 54 years, 55 to 64 years, 65 to 74 years, and ≥ 75 years. Renal function categories will 		

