7. RATIONALE AND BACKGROUND

Patients with type 2 diabetes mellitus (T2DM) have progressive decline in renal function and this decline in function is greater than age-related decline in patients without diabetes (1-4). Selection of glucose lowering agents is often affected by the level of renal function. Dipeptidyl peptidase-4 (DPP-4) inhibitors are approved to treat hyperglycemia among adults with T2DM with a wide range of renal function. In contrast to most other DPP-4 inhibitors (5), linagliptin does not require dose adjustment as renal function declines. Without further requirement of dose adjustment, linagliptin affords simplicity for chronic management of HbA1c.

Current literature indicate that decline in renal function is also associated with glycemic control, hypertension, albuminuria and dyslipidemia (9-11). However, there is limited evidence about the real world effectiveness and safety of linagliptin across different age and renal functions among adults with T2DM.

Data from clinical studies demonstrate that the expected reduction in HbA1c should be similar across the range of ages, but direct comparisons with younger patients are not available. Barnett et al reported on 238 patients aged 70 or older randomized to linagliptin 5 mg daily (n = 160) or placebo (n=78). The placebo adjusted mean difference in HbA1c after 24 weeks was -0.64% (95% CI -0.81 to -0.48) (12). Inzucchi et al reported on 247 patients aged 70 or older randomized to linagliptin (n = 126) or placebo (n = 121) added to basal insulin (13). The placebo adjusted mean difference in HbA1c after 24 weeks was -0.77 (94% CI -0.95 to -0.59). These values are consistent with other studies of linagliptin, but do not provide direct comparison data with younger patients.

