9. RESEARCH METHODS

9.1 STUDY DESIGN

This will be a non-interventional cohort study using existing data from patients in the Optum Clinical Database which contains electronic health record (EHR) data from providers across the United States.

Real-world EHR data will be used to determine whether there is comparable effectiveness of linagliptin 5 mg daily on glycemic effectiveness as determined by the change in HbA1c and the percentage of patients achieving an HbA1c goal of < 7.0% during the 60 to 180 days after initiation of linagliptin across a range of age and renal function categories.

[figure not shown]

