9.4 DATA SOURCES

This study will use data from Optum’s Clinical Electronic Health Record (EHR) database. This database aggregates clinical treatment data from a provider network of over 140,000 physicians at more than 600 hospitals and more than 6,500 clinics. The EHR database currently has more than 60 million unique patients across the United States and Puerto Rico. The demographics of patients within the Optum EHR data are representative of the United States population ([Table 3](#)).

The data are provided by more than 46 contributors, including the nation’s leading medical groups, integrated delivery networks (IDNs), and hospital chains. Using deterministic matching technology, Optum collects the provider data from different platforms and IT systems (e.g., Cerner, Epic, GE, McKesson), and then normalizes, validates, and integrates it. The result is a longitudinal record that delivers a comprehensive spectrum of health and medical information. Records in the database are updated quarterly.

Table 3. Optum EHR Data Patient Demographics Compared with the US Population

Attribute	Optum Lives, 2015	US Healthcare Utilizers ¹	US Population ²
Gender			
Male	43%	47%	49%
Female	57%	53%	51%
Age Group			
0-9	10%	13%	13%
10-17	7%	10%	11%
18-24	7%	8%	10%
25-34	12%	13%	14%
35-44	12%	12%	13%
45-54	14%	13%	14%
55-64	15%	14%	13%

¹ Source of US estimate of healthcare utilizers by age & sex: US Department of Health & Human Services, Agency for Healthcare Research & Quality, Medical Expenditure Panel Survey (MEPS), Projected Expenditure Data File for 2015. Percent of US population with non-zero medical expenditures found from MEPS and applied to US population estimate for 2015 from US Census Bureau, Current Population Survey.

² Source of estimate of US population totals alone and by insurance type: US Census Bureau, Current Population Survey, Annual Social and Economic Supplement, 2015.

Attribute	Optum Lives, 2015	US Healthcare Utilizers ¹	US Population ²
65-74	12%	9%	9%
75+	10%	8%	6%
US Region			
Northeast	13%		18%
Midwest	35%		21%
South	38%		37%
West	14%		24%
Race/Ethnicity			
White	62%	66%	62%
African American	9%	11%	12%
Hispanic	6%	16%	18%
Asian	2%	5%	5%
Other/Unknown	21%	3%	3%
Insurance Coverage			
Commercial	66%	61%	58%
Medicare	14%	17%	16%
Medicaid/ Other gov't	12%	13%	15%
Uninsured	8%	9%	10%

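### With no comparator and no equivalence margin, uncontrolled HbA1c change cannot support a conclusion that linagliptin is comparably effective across age and renal groups

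*Combined protocol and SAP*

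**What the plan says.** The stated objectives are modest. Section 8 makes the primary objective a description of HbA1c change by age and renal category, with comparisons as secondary objectives. Section 9.5 calls the study exploratory, without prior hypotheses.

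Other sections go further. Section 9.1 states: "Real-world EHR data will be used to determine whether there is comparable effectiveness of linagliptin 5 mg daily on glycemic effectiveness". Section 7 presents earlier pooled trial data as support for a proposal to show comparable effects across renal categories. The third limitation in Section 9.9 speaks of a claim of comparable glycaemic effectiveness. Section 9.7.1 mentions confirming statistical comparability. No section gives an equivalence margin or any other criterion for it.

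On the comparator, Section 9.9 says: "Since all other DPP4 inhibitors require dose adjustment for declining renal function, a comparator study to show similar/different effectiveness would be difficult to design". It refers to the patient factors that would have to be accounted for, and adds that such a study "likely would require an inordinately large data base". No calculation is given. On the same pharmacological fact, Section 7 says "In contrast to most other DPP-4 inhibitors (5), linagliptin does not require dose adjustment as renal function declines", and the abstract (Section 4) also says *most*.

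For analysis, Section 9.7.3 plans t-tests and chi-square tests. If cell sizes allow, it also plans an ordinary least squares (OLS) model of HbA1c change on age, sex, race, ethnicity, region, pre-index HbA1c, eGFR category, comorbidity score and individual comorbidities.

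**The concern.** Each patient's change is measured against that patient's own earlier value. It therefore contains the effect of linagliptin plus whatever else moved HbA1c over the same months: regression to the mean, closer follow-up, natural course, and other drugs. If these other components differ between eGFR or age groups, the comparison across groups attributes the difference to linagliptin. A flat pattern could hide a drug effect that falls with eGFR, and a sloping pattern could appear when the drug effect is equal.

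The trial results cited in Section 7 for older patients, and in Section 9.9 for long-standing diabetes, are placebo-adjusted. Nothing in this design plays that part. Section 12 wants the results in the public domain to answer outside questions, so the wording of the conclusion matters.

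**Working it through.** **1. The plan's own sample size.** Inputs from Section 9.5: difference 0.5 points, SD 1.2 or 1.5, 80% power, two-sided alpha 0.05. The normal formula is n per group = 2 × (1.960 + 0.842)² × SD² / 0.5². It gives 90.4 (SD 1.2) and 141.3 (SD 1.5). The two-sample t-test version gives 91.39 and 142.25, which round up to the stated 92 and 143. The calculation is for detecting a difference, not for showing similarity.

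**2. What a non-significant result would mean.** The half-width of the 95% interval for a difference between two groups is 1.96 × SD × √(2/n).
- n = 92, SD 1.2: 1.96 × 1.2 × 0.1474 = 0.35 points.
- n = 143, SD 1.5: 1.96 × 1.5 × 0.1183 = 0.35 points.

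At the minimum size, an observed difference of 0.3 points would be non-significant, with an interval from about −0.05 to 0.65. That interval includes the 0.5 points the study was sized to detect.

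**3. Larger groups do not remove the bias.** Section 9.7.1 reports more than 2,500 patients in the smallest age cell at the feasibility stage. With n = 2,500 the half-width is 1.96 × 1.2 × 0.0283 = 0.07 (SD 1.2) or 0.08 (SD 1.5). At that precision, random error is smaller than a modest bias.

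**4. What enters the contrast.** For two groups g and h, the observed difference is (drug effect g − h) + (non-drug change g − h) + (added-therapy effect g − h). The documents give no size for the last two terms. If what remains of them after adjustment is assumed to be 0.1 to 0.3 points, that is 0.1/0.5 = 20% to 0.3/0.5 = 60% of the sizing difference.

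**5. What the planned adjustment covers.** Section 9.9 accepts that change depends on baseline HbA1c. With an assumed baseline gap of 0.5 points and an assumed slope of 0.3 to 0.6, baseline alone would produce a difference of 0.15 to 0.30 points in the unadjusted t-tests. The OLS model can remove that part because it includes pre-index HbA1c. Several things lie outside it:
- Its covariate list has no background antihyperglycaemic therapy (although Section 9.3.3.2 captures it), no added therapy and no diabetes duration.
- Section 9.2.3 keeps patients who add drugs in follow-up, and says linagliptin discontinuation cannot be measured accurately.
- Section 9.2.3 sends the added-drug sensitivity analysis to Section 9.7.4.4. The contents list ends its data-analysis entries at 9.7.3 and the available text has no such section, so its effect cannot be judged.
- The model itself is conditional on sample size.

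**6. The two reasons for having no comparator.** Section 9.9 writes "Since all other DPP4 inhibitors require dose adjustment for declining renal function"; Section 4 writes "In contrast to most other DPP-4 inhibitors, linagliptin does not require dose adjustment as renal function declines". *All* and *most* cannot both stand.

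On database size, an illustrative drug-by-renal-band contrast with four equal cells needs 4 × (1.960 + 0.842)² × SD² / δ² per cell.

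| δ (points) | SD 1.2 | SD 1.5 |
|---|---|---|
| 0.5 | 181 | 283 |
| 0.3 (assumed) | 503 | 785 |
| 0.1 (assumed) | about 4,521 | about 7,064 |

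At 0.5 points, five bands and two drugs would need 10 × 181 = 1,810 to 10 × 283 = 2,830 patients. Section 9.7.1 counts 13,962 linagliptin patients with the key data, an average of 13,962/5 = 2,792 per band. Whether the size argument looks weak therefore depends on δ. The calculation is unadjusted, and the documents give no eGFR or comparator counts.

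**The case against.** The strongest reply is that the plan already handles this. The missing comparator is a declared limitation, the study is labelled exploratory, the primary objective only describes, and the objectives already speak of change following initiation. A multivariable model is planned. All of this is true, and it is why the remedy is limited to wording. It does not license the stronger aim in Section 9.1 or the matching language in Sections 7 and 9.9.

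Three stronger readings are tempting and are not supported:
- *Both reasons for having no comparator are contradicted by the plan.* Only the first is. The second is hedged and concerns a comparison that accounts for many patient factors. The figure in "The EHR database currently has more than 60 million unique patients across the United States and Puerto Rico" counts everyone in the database, whereas linagliptin prescriptions covered 63,499 patients. Section 9.7.1 also warns that some cells, such as eGFR 30 to 44, may be too small. The size reason is unsupported by a calculation, not refuted.
- *A cohort starting other DPP-4 inhibitors should be added.* That would give a between-drug difference, not the effect of linagliptin. If both effects fell with eGFR, the contrast would stay flat. Section 7 says drug choice is often affected by renal function, so channelling is likely, and on the plan's own account dosing of most comparators changes with renal function.
- *Any non-drug difference passes in full into the result.* The part explained by pre-index HbA1c, demographics and comorbidity would be removed if the model is fitted.

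**Conclusion.** The concern holds for the conclusion the plan intends to draw, not for the decision to run a single-cohort study. A descriptive report of HbA1c change by age and renal group is sound within its stated limits. A statement of comparable linagliptin effectiveness is not, for two separate reasons: uncontrolled change does not isolate the drug effect, and no margin exists against which similarity could be judged.

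The second reason has a calculable size: about 0.35 points either side of the estimate at the plan's minimum group sizes, taking its SDs as correct and groups as equal. The first does not. The 0.1 to 0.3 points is an assumption used only for scale, and its direction is unknown.

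The conflict between *all* and *most* is clerical but real. It bears on the first stated reason for having no comparator.

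**What to change.** 1. In Sections 7, 9.1 and 9.9, restrict the intended conclusion to *HbA1c change after starting linagliptin, by age and renal group*, in line with the primary objective.
2. State in Section 9.9 that comparable effectiveness will not be concluded from uncontrolled change or from non-significant p-values.
3. Reconcile Section 9.9 with Sections 4 and 7 on whether all or most other DPP-4 inhibitors need dose adjustment.
4. Support the database-size reason in Section 9.9 with a calculation, or soften it to a judgement.

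No comparator cohort is required. Items 1 to 3 are text edits; item 4 is a text edit or one short calculation. No new data are needed, and the planned analyses stay as they are. The real cost is a less favourable headline claim.
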